After the time of Discharge on the Day 90 Visit (Day 91), subject will enter a 28-day safety follow-up period during which there will be recording of spontaneously reported new AEs/SAEs and the active follow-up of ongoing AEs/SAEs by the study site. In

general, all AEs will be followed-up until resolved, stabilized (i.e., no worsening of the event), or a plausible explanation for the event has been found. The end of the study (EOS) is defined as the time of Discharge on Day 90 Visit (Day 91) plus 28-day follow-up.

Study Population and Main Criteria for Inclusion:

Female or male smoking, apparently healthy adult subjects without any restriction to races and ethnicities, meeting the following main inclusion criteria:

- Subject is aged with a minimum of 22 years(inclusive).
- Smoking, apparently healthy subject as judged by the Investigator.
- Subject smokes at least 10 commercially available mCC per day (no brand restrictions) for the last 4 weeks, based on self-reporting.
- Subject has smoked for at least the last 3 consecutive years.
- Subject does not plan to quit smoking within the next 6 months.
- Subject is ready to comply with the study protocol (e.g., to accept interruption of smoking for up to 91 days and to use THS 2.2 Menthol).

Investigational Products; Dose; and Mode of Use:

Test Product:

Tobacco Heating System 2.2 Menthol (THS 2.2 Menthol).

Reference Product:

The reference product to the THS 2.2 Menthol during the randomized exposure period is the subject's own preferred commercially available single brand of mCC.

Reference Point: SA.

Sample size:

Approximately one hundred and sixty smokers in the full analysis set (FAS) (~80 in THS 2.2 Menthol arm, ~40 in mCC and ~40 in SA) are required to attain 80% power to show at least a 50% reduction for any of the selected primary BoExp in THS 2.2 Menthol compared to the mCC arm, using a one-sided test with 2.5% type I error probability.

Data and information contained in this document are considered to constitute trade secrets and confidential commercial information, and the legal protections provided to such trade secrets and confidential information are hereby claimed under the provisions of United States law. No part of this document may be publicly disclosed without the written consent of Philip Morris International.

Statistical Methods:

Primary confirmatory endpoint: The hypothesis to be tested is that the geometric mean level of the BoExp for THS 2.2 Menthol is lower relative to mCC.

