3.4.1 Primary Endpoints

- To demonstrate the reduction of primary BoExp to HPHCs (except Total NNAL) in a confinement setting in smokers switching from mCC to THS 2.2 Menthol as compared to smokers continuing to smoke mCC.
 - MHBMA, 3-HPMA, S-PMA (concentration adjusted for creatinine) in 24-hour urine, and COHb in blood (expressed as % of saturation of hemoglobin) as measured on Day 5.
- To demonstrate the reduction of Total NNAL in an ambulatory setting in smokers switching from mCC to THS 2.2 Menthol as compared to smokers continuing to smoke mCC.
 - Total NNAL level (concentration adjusted for creatinine) in 24-hour urine fraction as measured on Day 90 Visit.

Evaluation criterion:

The study will be considered successful if the study demonstrates a 50% reduction or more in MHBMA, 3-HPMA, S-PMA, and COHb at Day 5 and in Total NNAL at Day 90 Visit in smokers switching from mCC to THS 2.2 Menthol as compared to smokers continuing to smoke mCC, using a one-sided test with 2.5% type I error probability.

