Data and information contained in this document are considered to constitute trade secrets and confidential commercial information, and the legal protections provided to such trade secrets and confidential information are hereby claimed under the provisions of United States law. No part of this document may be publicly disclosed without the written consent of Philip Morris International.

Table 23 describes the expected power to demonstrate a reduction on 5 primary BoExp in smokers switching from CC to THS 2.2 Menthol as compared to those continuing to smoke mCC, using one-sided test with 2.5% type I error probability using the assumptions from YVD-CS01-EU and ZRHX-EX-01 given a sample size of 160 smokers (~80 in THS 2.2, ~40 in CC, and ~40 in the SA arm). Therefore subjects will be enrolled into the study until there are 160 smokers in the FAS population.

Table 23. Expected power (YVD-CS01-EU and ZRHX-EX-01 studies assumptions)

Assumptions	Reduction					
	50%	51%	52%	53%	54%	55%
YVD-CS01-EU	94%	88%	81%	70%	56%	38%
ZRHX-EX-01	98%	97%	92%	76%	41%	6%

Power considerations related to secondary endpoints of biological changes:

The sample size is sufficient to obtain 95% CIs for the ratio between (geometrical) mean levels of primary BoExp in THS 2.2 Menthol and SA with upper and lower limits deviating not more than 18% from the point estimates, with an 80% overall probability of achieving the desired precision of estimating the true mean.

This study has 80% power using a one-sided test with 2.5% type I error probability:

- To detect a 0.631 [mL/min/kg] (29%) difference between THS 2.2 Menthol and mCC in CYP1A2 activity, as measured by the caffeine clearance, assuming a SD of 0.564. Effect size and variability are derived from data obtained in the YVD-CS01-EU study sponsored by PMI.
- To detect a 24.71 [ng/g creatinine] (20%) difference between THS 2.2 Menthol and mCC in 11-DTX-B2, assuming a SD of 43.78, as reported by Saareks et al., 2001. The anticipated effect size of THS 2.2 Menthol is assumed to be about 90% of the effect of smoking cessation reported in the paper by Saareks et al., 2001.

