12.5 Primary Analysis

12.5.1 Primary Endpoint Analysis Variables

The primary endpoints are:

- COHb on Day 5
- MHBMA on Day 5
- 3-HPMA on Day 5
- S-PMA on Day 5
- Total NNAL on Day 90.

See Section 3.4.1.

Evaluation criterion:

The study will be considered successful, if the study demonstrates a 50% reduction or more for all five primary BoExp in the THS 2.2 Menthol arm compared to the mCC arm, using a one-sided test with 2.5% type I error probability.

Data and information contained in this document are considered to constitute trade secrets and confidential commercial information, and the legal protections provided to such trade secrets and confidential information are hereby claimed under the provisions of United States law. No part of this document may be publicly disclosed without the written consent of Philip Morris International.

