12.5.4 Confirmatory Analysis

The hypothesis to be tested is that the geometric mean level of the BoExp for THS 2.2 Menthol is lower relative to mCC.

For primary BoExp, the hypothesis will be tested on Day 5 for monohydroxylbutenyl-mercapturic acid (MHBMA), 3-hydroxypropylmercapturic acid (3-HPMA), S-phenylmercapturic acid (S-PMA), and carboxyhemoglobin (COHb), and on Day 90 Visit for Total NNAL.

The transformed BoExp data on a natural log scale will be analyzed by means of a generalized linear model using product arm as covariate adjusting for the following baseline information: sex, average cigarette consumption over the previous 4 weeks, and baseline value of endpoint. The test will be declared significant if the contrast THS 2.2 Menthol vs mCC is significant. Estimates of differences between groups will be back-transformed to provide relative effects.

Assumptions of the analysis of variance model will be tested. Markedly non-lognormally distributed BoExp data will be transformed or analyzed by appropriate non-parametric methods.

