12.6.4 Inferential Analysis

For the secondary BoExp and selected risk markers, the hypothesis to be tested is the same as described in Section 12.5.4. This will be tested for secondary BoExp on Day 5, and if significant, on Day 90.

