#### 5.5 Study Hypotheses And Evaluation Criteria

##### 5.5.1 Hypotheses

The hypothesis to be tested is that the geometric mean level of the BoExp for THS 2.2 Menthol is lower relative to mCC.

For the primary analyses, the hypothesis will be tested on Day 5 for MHBMA, 3-HPMA, S-PMA, and COHb, and on Day 90 Visit for Total NNAL according to the primary and secondary objectives. For the secondary BoExp, the hypothesis will be tested on Day 5, and if significant on Day 90 Visit.

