##### 5.5.2 Evaluation Criteria

The study will be considered successful if the study demonstrates a 50% reduction or more in MHBMA, 3-HPMA, S-PMA, and COHb on Day 5, and in Total NNAL at the Day 90 Visit in smokers switching from mCC to THS 2.2 Menthol as compared to smokers continuing to smoke mCC, using a one-sided test with 2.5% type I error probability.

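### The primary contrast, its SAS code and its one-sided p-value test a THS:mCC ratio of 1, while study success and the stated power need a test against 0.5; nothing in the plan links the two.

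*Protocol*

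**What the plan says.** Two different null values appear.

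**Ratio 1.** SAP 5.5.1 states: "The hypothesis to be tested is that the geometric mean level of the BoExp for THS 2.2 Menthol is lower relative to mCC". Protocol 12.5.4 and SAP 12.6.1.2 use the same hypothesis, and Protocol 12.5.4 adds the decision rule: "The test will be declared significant if the contrast THS 2.2 Menthol vs mCC is significant". SAP 12.6.1.1 implements it in PROC GLM as the least-squares-mean difference from the mCC control, with no offset. It then tabulates the back-transformed ratio, a two-sided 95% CI and a one-sided p-value whose null is not named. SAP 12.6.1.3 repeats the contrast in PROC MIXED.

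**Ratio 0.5.** Protocol 12.5.1: "The study will be considered successful, if the study demonstrates a 50% reduction or more for all five primary BoExp", by a one-sided 2.5% test. Protocol 3.4.1 and SAP 5.5.2 agree ("The study will be considered successful if the study demonstrates a 50% reduction or more"). The synopsis sizes the trial on the same target: its numbers "are required to attain 80% power to show at least a 50% reduction for any of the selected primary BoExp in THS 2.2 Menthol". The power table in Protocol 12.2 and SAP 8 uses that target too.

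**Closed procedure.** Protocol 12.1.5 (one-sided 2.5%) and SAP 12.1.7 (5%, sidedness not given) make any confirmatory claim depend on statistical significance for all primary endpoints. Neither names the null.

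**The concern.** The sections that define the confirmatory test carry no margin. Protocol 12.6.4 confirms this: "For the secondary BoExp and selected risk markers, the hypothesis to be tested is the same as described in Section 12.5.4". Those secondary endpoints have no 50% requirement, so the hypothesis they share with the primary endpoints cannot contain one.

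Run as written, the primary table therefore shows a p-value that does not test the claim defining success. The closed procedure refers to significance, and the only significance rule for the primary contrast is the one against ratio 1. The same table is a topline output (SAP 13.3) and is to be considered for ClinicalTrials.gov (SAP 13.5), where its p-value could be read as support for the 50% claim.

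**Working it through.** **Inputs.** Expected mean ratios (MR) and CVs are from Protocol 12.2: Table 19 (YVD-CS01-EU), Table 20 (Total NNAL, used in both sets) and Table 21 (ZRHX-EX-01). Analysed sizes are from Table 22: 80:40 for the four Day 5 endpoints and 40:40 for Total NNAL. The level is one-sided 2.5%.

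**Formulas.** SD = sqrt(ln(1 + CV²)); SE = SD × sqrt(1/n₁ + 1/n₂); df = n₁ + n₂ − 2. Power against a null ratio R comes from the noncentral t with noncentrality ln(R/MR)/SE. Joint power is the product over five endpoints, assuming independence.

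**1. Reproduce the stated power (50% column of Table 23: 94% and 98%).**

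- COHb, YVD: SD = sqrt(ln(1 + 0.32²)) = 0.312; SE = 0.312 × sqrt(1/80 + 1/40) = 0.0605; ln(0.5/0.40)/SE = 0.223/0.0605 = 3.69; power 0.9555.
- COHb, ZRHX (MR 0.44, CV 0.14): power 0.9969.
- Total NNAL (MR 0.30, CV 0.60, 40:40): SE = 0.124; power 0.9825.
- 3-HPMA, MHBMA, S-PMA: each at least 0.9998 in both sets.
- Joint power against 0.5: 0.9386 (YVD) and 0.9795 (ZRHX), matching 94% and 98%.
- Joint power against 1: above 0.9999 in both sets.

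So the stated figures are the power of a test against 0.5. Only the 50% column is used here; several of the 52% to 55% columns do not reproduce within two points from the printed inputs, which does not bear on this point.

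**2. Largest observed ratio that passes each test.** Against 1 it is exp(−t × SE); against 0.5 it is half that. For COHb, t = 1.980, so exp(−1.980 × 0.0605) = 0.887.

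| Endpoint (YVD CVs) | SE | Significant against 1 up to | Significant against 0.5 up to |
|---|---|---|---|
| COHb | 0.0605 | 0.887 | 0.444 |
| 3-HPMA | 0.0915 | 0.834 | 0.417 |
| MHBMA, S-PMA | 0.1223 | 0.785 | 0.392 |
| Total NNAL | 0.124 | 0.781 | 0.391 |

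An observed COHb reduction of 11% passes the written contrast; about 56% is needed to demonstrate 50%.

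**3. How often the two tests part company.**

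- At the planning assumptions the ratio-1 test almost always rejects, so the disagreement rate is 1 minus the power against 0.5: 1 − 0.9386 = 6.1% (YVD) and 1 − 0.9795 = 2.1% (ZRHX) over the five endpoints.
- If every true ratio were 5% higher than assumed (my assumption, for example 0.42 instead of 0.40 for YVD COHb), joint power against 0.5 falls to 0.780 and 0.793, and disagreement rises to about 22% and 21%.
- If every true ratio were exactly 0.50, all five written contrasts are significant together in more than 99.9% of trials, while a test against 0.5 passes each endpoint in 2.5%.
- If every true ratio were 0.60, which misses the criterion, all five written contrasts are still significant together in about 95% (YVD) or 98% (ZRHX) of trials.

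**The case against.** The strongest reply is that the 0.5 test is already in the plan. Protocol 12.5.1 sits in the same parent section as 12.5.4, and SAP 5.5.2 directly follows the hypothesis; both give margin, level, sidedness and the all-five rule. Comparing the upper limit of the planned two-sided 95% CI with 0.5 is exactly that one-sided 2.5% test. No section equates a significant contrast with success. The documents could be read as two deliberate layers: a directional hypothesis and a stricter success criterion. The disagreement rates under the planning assumptions, and under ratios 5% higher, are ordinary type II error of the 0.5 test. The null of the one-sided p-value is inferred from the hypothesis and code, since the code's default output is two-sided and the conversion is not shown.

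Most of this stands as description. The intent is visible, the right decision can be made from planned output, and the rates in step 3 are decision errors only if the p-value is read as meeting the 50% criterion. What does not stand is the conclusion that nothing needs fixing. A reader must still infer that the CI, and not the tabulated p-value, decides success. The closed procedure invokes significance without saying against what, and the code given for the primary analysis does not compute the test that was powered. Converting to one side does not move the null from 1.

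**Conclusion.** The concern holds and should be fixed. The success criterion is not missing; the link is. The written hypothesis, contrast and code test a ratio of 1, while success and the 94% and 98% power rest on 0.5. The gap between passing thresholds is a factor of two on every endpoint (COHb 0.887 against 0.444 under the YVD assumptions).

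The figures assume log-normal data, the printed ratios and CVs, the planned per-protocol sizes, no variance reduction from the covariates and, for joint power, independence between endpoints. The mismatch itself depends on none of these. As a smaller matter, SAP 12.1.7 should state its sidedness to agree with Protocol 12.1.5.

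**What to change.** - In Protocol 12.5.4 and SAP 5.5.1, 12.6.1.1 and 12.6.1.2, state for each primary biomarker H0: THS:mCC geometric mean ratio ≥ 0.50 against H1: ratio < 0.50.
- Declare success only if the upper limit of the two-sided 95% CI is below 0.50 on all five, and say that significance in the closed procedure means significance against 0.50.
- Compute the tabulated one-sided p-value against ln(0.5), in the primary model and in the SAP 12.6.1.3 sensitivity analyses.
- Label any test of lower than mCC separately as not establishing success, and point Protocol 12.6.4 to that directional hypothesis for secondary endpoints.
- In SAP 12.1.7, give the level as one-sided 2.5%.

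The cost is SAP wording, about one line of code per model, and a protocol wording amendment with the approvals in Protocol 1.1. No new data or subjects are needed, and the sample size and the 50% power column do not change.

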12.6 Secondary Analysis

12.6.1 Secondary Endpoint Analysis Variables

See Section 3.4.2.

More details on derivation rules will be given in the SAP.

12.6.2 Baseline Comparability

Not applicable.

12.6.3 Descriptive Analysis

In general, secondary endpoints will be summarized as described in Section 12.1.3 on the FAS.

12.6.4 Inferential Analysis

For the secondary BoExp and selected risk markers, the hypothesis to be tested is the same as described in Section 12.5.4. This will be tested for secondary BoExp on Day 5, and if significant, on Day 90.

12.6.5 Safety Analysis

In general, all safety data will be listed and tabulated on the safety population by study arm, using the approach described in Section 12.1.3. Safety variables collected during exposure periods will also be reported by product exposure.

Adverse event data will serve as the primary assessment of safety. Other safety variables monitored in this study include: respiratory symptoms (cough assessment VAS and Likert scales); vital signs (systolic and diastolic blood pressure, pulse rate, respiratory rate); electrocardiogram (ECG) data; clinical chemistry, hematology, concomitant medications, and urine analysis safety panel; physical examination.

The number and percentage of subjects with AEs and SAEs will be tabulated by system organ class (SOC) and preferred term (PT). Summaries will also be presented for AEs leading to withdrawal, AEs leading to death, AEs by relatedness to product exposure, AEs by severity, and laboratory AEs. Tabulations will be performed for both the number of subjects experiencing an event and the number of events.

The number and percentage of subjects with clinical findings by sequence for laboratory parameters will be summarized for the safety population. Shift tables showing change from baseline of clinical findings will be provided for: ECGs, physical examinations and laboratory parameters (both shifts in normal ranges and toxicity grades). Descriptive statistics will be summarized by visit and change from baseline for laboratory parameters, ECG, respiratory symptoms, and vital signs.

12.7 Exploratory Analysis

12.7.1 Exploratory Endpoint Analysis Variables

See Section 3.4.3.

12.7.2 Descriptive Analysis

In general, exploratory endpoints will be summarized as described in Section 12.1.3 on the FAS.

12.8 Demographics and Baseline Characteristics

Demographic and other baseline characteristics will be reported for FAS and safety population. Summary statistics will be provided by exposure group and stratified by sex and by cigarette consumption. Formal statistical analysis will not be performed on baseline demographic data.

12.9 Interim Analysis

There are no planned interim analyses.

12.10 Preference Analysis

At admission, subjects will be asked for their preferred product (THS 2.2 Menthol, mCC, SA, or no preference). A sensitivity analysis will be run for the exposure according to the subjects' preferred product.

13.2 Subject Confidentiality

All information obtained during the conduct of the study with respect to the subjects' state of health will be regarded as confidential. A statement to this effect will be written in the information provided to the subject. An agreement to disclose any such information will be obtained from the subject in writing and signed by the subject, in compliance with all local and national data protection and privacy legislation.

The anonymity of subjects participating in this study will be maintained. Subjects will be identifiable by the Sponsor (or Sponsor's authorized representative) on eCRFs and other documents by their subject (or randomization) number/code, sex, and date of birth, but not by name, initial, or any other details relating to identifiable person (e.g., address, social security number, medical chart number, etc.). The assignment of a subject number/code for subject identification will be based on the appropriate data protection rules.

The blood samples for transcriptomics and the data related to these samples will be anonymized. Anonymized data and samples are initially single or double coded where the link between the subjects' identifiers and the unique code(s) is subsequently deleted. This is applicable for the blood bio-banking for transcriptomics only.

Any documents that allow full identification of the subject (e.g., the subject's signed Study Information Sheet and ICF) must be maintained in confidence by the Investigator. If any document relating to this study shows a subject's name or any other details relating to an identifiable person (e.g., address, social security number, medical chart number, etc.), the name or other identifiable details must be obscured before a copy of that document is supplied to the Sponsor or the Sponsor's authorized representative.

13.3 Access to Source Documentation

Subjects will be informed that, during the course of the clinical study, the Sponsor, any authorized representatives of the Sponsor, IRB, or regulatory authorities may inspect their medical records to verify the information collected, and ensure that all personal information made available for inspection is handled in the strictest confidence and in accordance with national and local data protection and privacy legislation.

The Investigator and all study site staff involved with the study must permit direct access to source data/documents for study related monitoring, audits, IRB review, and regulatory inspection(s).

13.4 Record Retention

All records of data, source data and Source Documents (original records or certified copies), in any form (including, but not limited to, written, electronic, magnetic, optical records and

Data and information contained in this document are considered to constitute trade secrets and confidential commercial information, and the legal protections provided to such trade secrets and confidential information are hereby claimed under the provisions of United States law. No part of this document may be publicly disclosed without the written consent of Philip Morris International.

scans, X-rays, and ECGs) that describe or record the methods, conduct, and/or results of the study, the factors affecting the study, and the actions taken will be maintained by the Investigator/study site for the study, as required by ICH GCP and any other applicable local or national regulations. For X-rays, at least the radiologist's assessment is required as source documentation. If the actual image is available, it can be stored on CD as well.

Essential study documents/records, which individually and collectively permit evaluation of the conduct of a study and the quality of the data produced, are described in Section 8 of the ICH Tripartite Guideline for Good Clinical Practice (ICH Guideline for Good Clinical Practice E6 (R1), July 1996).

Essential documents must be retained by the Investigator for a minimum of:

- At least 15 years after completion or discontinuation of the study, or
- At least 2 years depending on, for example, the circumstances
- After formal discontinuation of clinical development of the IP.

These documents should be retained for a longer period, however, if required by the applicable regulatory requirements or by an agreement with the Sponsor.

Examples of essential records/documents include, but are not limited to:

- Signed informed consent documents for all subjects and Master ICF/Subject Information Sheet.
- Subject identification code list, Screening Log, and Enrolment Log (if applicable).
- Record of all communications between the Investigator and the IRB, composition of the IRB.
- Record of all communications/contact between the Investigator, Sponsor, and its authorized representatives.
- List of sub-Investigators and other appropriately qualified persons to whom the Investigator has delegated significant study-related duties, together with their roles in the study, curricula vitae, and their signatures.
- Investigator Logs.
- eCRFs, study specific questionnaires (and associated data/scoring), subject diaries.
- AE reports and details of follow-up investigations, details of concomitant medication.
- All other Source Documents (e.g., chest X-rays, ECGs, consultation reports, physical examination, laboratory records) or any electronically captured study source data.
- Clinical laboratory reports, laboratory normal ranges.

Data and information contained in this document are considered to constitute trade secrets and confidential commercial information, and the legal protections provided to such trade secrets and confidential information are hereby claimed under the provisions of United States law. No part of this document may be publicly disclosed without the written consent of Philip Morris International.

- Original medical/hospital records, if applicable (the medical files of study subjects must be retained in accordance with local legislation and in accordance with the maximum period of time permitted by the hospital or study site).
- Record of any body fluids or tissue samples collected and retained.
- Device Issue Log, IP Accountability Logs, dispensing records.
- Information regarding subjects' discontinuation and any follow-up.

It is the responsibility of the Sponsor to inform the Investigator/study site as to when these documents no longer need to be retained.

The Investigator/study site must take measures to prevent accidental or premature destruction of these documents.

If an Investigator wishes to assign the study records to another party or move them to another location, the Sponsor must be notified in advance.

The Investigator must obtain written approval from the Sponsor before destruction of any records. Normally, these records will be held in the Investigator's archives. If an Investigator is unable to meet this obligation, they must ask the Sponsor for permission to make alternative arrangements. Details of these arrangements must be documented.

The Sponsor or Sponsor's authorized representative will maintain documentation relating to the study as long as the IP is on the market, and/or for 15 years after the CSR has been finalized.

